7 STUDY INTERVENTIONS DISCONTINUATION AND PARTICIPANT DISCONTINUATION/WITHDRAWAL

7.1 DISCONTINUATION OF STUDY INTERVENTIONS

The Sponsor, SDRT, PI, approving HREC(s), and the TGA independently reserve the right to discontinue the trial at any time for safety or other reasons. This will be done in consultation with the Sponsor where practical. In the event of premature trial termination or suspension, the above-mentioned parties will be notified in writing by the terminator/suspender stating the reasons for early termination or suspension (with the exception of the TGA as it is the Sponsor's responsibility to notify regulatory authorities). After a decision to prematurely terminate the trial or to suspend the trial, the Sponsor and the PI will ensure that adequate consideration is given to protecting the participants' interest and safety. The PI must review all participants as soon as practicable and complete all required records.

7.1.1 CRITERIA FOR ADMINISTRATION OF RESCUE MEDICATION INSTEAD OF IMP DOSING ON DAY 8

Once inoculated, it is expected that some study participants will experience malaria symptoms and biological changes (i.e. mild ALT/AST elevation, mild decrease in neutrophil count). Therefore, the following criteria should be considered as guidance for the decision not to proceed with pyronaridine dosing on Day 8 and preference for rescue medication instead:

1. A participant experiences an SAE or \geq CTCAE Grade 3 event (e.g. inoculum-related events such as lymphopenia or neutropenia).
2. A participant has an ALT or AST $> 2 \times$ ULN or total bilirubin $> 1 \times$ ULN.
3. A participant with positive alcohol or urine drug screen.
4. A participant who tests positive for SARS-CoV-2 (section 8.3.7).
5. A participant with one of the following ECG abnormalities:
 - QTcF at any time >480 msec,
 - Bundle branch block (except right bundle branch block that was present prior to pyronaridine administration),
 - Any arrhythmia, except:
 - a. *Sinus bradycardia that is clinically asymptomatic, and not associated with any other relevant ECG abnormalities,*
 - b. *sinus tachycardia that is clinically asymptomatic, and not associated with any other relevant ECG abnormalities,*
 - c. *Respiratory sinus arrhythmia,*
 - d. *Wandering atrial pacemaker,*

- e. *Isolated, single premature atrial/ventricular complex (i.e., no bigeminy, trigeminy, couplets, triplets or salvos) that does not occur more than once in a particular ECG tracing.*

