9.4.4 SAFETY ANALYSES

All descriptive statistics for safety parameters will be evaluated using the Safety Set.

All AE data will be listed for each volunteer, including severity, relationship to IMP (pyronaridine and malaria challenge agent), relationship to non-IMP protocol-specific treatments, outcome and actions taken. In addition, listings of AEs leading to discontinuation of the study, AESIs, SAEs and deaths, will be provided as applicable. Adverse events (AE) will be coded according to MedDRA and grouped by SOC and PT.

The main AE summaries will be restricted to Treatment Emergent Adverse Events (TEAEs) only, where a TEAE is defined as an AE that commences on, or after, the first administration of IMP up to the end-of-study (EOS) visit (inclusive). TEAEs without an onset date or time will be defined as treatment emergent except if an incomplete date (e.g., month and year) clearly indicates that the event started prior to first administration of IMP, or if the AE stop date indicates that the event stopped prior to the first administration of IMP.

At a minimum, the following AE summary tables will be provided:

- Overall summary of AEs
- All TEAEs
- TEAEs by severity
- TEAEs by relationship to the IMP
- TEAEs by relationship to rescue medications
- Serious TEAEs
- TEAEs leading to study withdrawal
- AESIs
- All Inoculation Period AEs
- Inoculation Period AEs by relationship to the malaria challenge agent

Lab parameters, physical examination, Body measurements, vital signs, Beck Depression inventory score and 12-lead ECG will be listed for all participants and visits. Summary tables for each scheduled visit, including observed values, change from each baseline and clinical significance of each abnormal value, will be presented.

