5.1 Analysis Set Descriptions

5.1.1 *Full Analysis Set*

The Full Analysis Set (FAS) will consist of all enrolled participants, i.e. participants that received the malaria challenge agent.

5.1.2 *IMP Set*

The IMP Set will include all enrolled participants administered with the IMP.

5.1.3 *PK Analysis Set*

The PK analysis set will include all participants with at least one available valid (i.e. not flagged for exclusion) PK concentration measurement, who received any study treatment and experienced no protocol deviations with relevant impact on PK data.

5.1.4 *PD Analysis Set*

The PD analysis set will include all participants inoculated with the malaria challenge agent and who develop parasitaemia detectable by qPCR, received a dose of pyronaridine, and have no protocol deviations or other circumstances that would exclude them from the PD analysis.

5.1.5 *PK/PD Analysis Set*

The PK/PD analysis set will include all participants from the PK set and all participants from the PD set.

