11.3.3 Laboratory

Parameters

Hematology

- Basophils (absolute)
- Eosinophils (absolute)
- Haematocrit
- Haemoglobin
- Lymphocytes (absolute)
- Monocytes (absolute)
- Neutrophils (absolute)
- Platelet count
- Red blood cell count
- White blood cell count

Biochemistry

- Alanine Aminotransferase (ALT)
- Albumin
- Alkaline phosphatase (ALP)
- Aspartate Aminotransferase (AST)
- Bicarbonate
- Bilirubin (direct)
- Bilirubin (total)
- Calcium
- Calculated eGFR (CKD-EPI)
- C-Reactive protein
- Chloride
- Cholesterol Total
- Creatinine
- Creatine kinase
- Gamma Glutamyl Transpeptidase (GGT)
- Glucose (random and fasting)
- Glucose-6-phosphatase (G6PD)
- Lactate dehydrogenase (LDH)
- LDL
- HDL
- Phosphate
- Potassium
- Protein Total
- Sodium
- Triglyceride
- Troponin T/high sensitivity
- Urea
- Uric Acid

Pregnancy Test and FSH

β-Human Chorionic Gonadotropin (β-HCG) (women of child bearing potential only)
Follicular Stimulating Hormone (FSH) (post-menopausal women only)

Urinalysis

Dipstick Testing	Quantitative Assessments	Urine Chemistry
Red blood cells	Red blood cells	Glucose
Glucose	White blood cells	Protein
Ketone		
White blood cells		
Protein		
pH		
Red blood cells		
Glucose		
Ketone		

Coagulation

- International Normalized Ratio (INR)
- Activated Partial Thromboplastin Time (APTT)

Serology

- Hepatitis B surface antigen (HB sAG)
- Hepatitis C antibodies
- Red blood cell antibodies
- Anti-hepatitis B core antibodies (anti-HBc Ab)
- Human Immunodeficiency Virus (HIV) Ag/Ab 1/2 (anti-HIV1 and anti-HIV2 Ab)

Biostatistical methods

Listings

All laboratory parameters and change from treatment baseline values will be presented in data listings. Values outside the laboratory reference range will be listed with flags if considered low or high for values outside the reference ranges (where applicable) and if values considered to be clinically significant by the investigator.

Pregnancy test data will be listed only, for all women. FSH data will be listed only, for all post-menopausal women.

Coagulation data as well as qualitative and quantitative urinalysis data will also be listed only.

Tables

Haematology, biochemistry and continuous dipstick urinalysis laboratory data will be summarised for each scheduled visit, including observed values, absolute change from treatment baseline

Categorical dipstick urinalysis results will be summarised for each scheduled visit using frequency tabulations.

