Overall Summary of Treatment Emergent Adverse Events	IMP
Summary of Inoculum Emergent Adverse Events by MedDRA System Organ Class and Preferred Term	FAS
Summary of Treatment Emergent Adverse Events by MedDRA System Organ Class and Preferred Term	IMP
Summary of Inoculum Emergent Adverse Events by Maximum Severity	FAS
Summary of Treatment Emergent Adverse Events by Maximum Severity	IMP
Summary of Inoculum related Treatment Emergent Adverse Events by MedDRA System Organ Class, Preferred Term	FAS
Summary of IMP Related Treatment Emergent Adverse Events by MedDRA System Organ Class, Preferred Term	IMP
Summary of Inoculum Related IAEs by System Organ Class, Preferred Term and Maximum Severity	FAS
Summary of IMP Related TEAEs by System Organ Class, Preferred Term and Maximum Severity	IMP

Inoculum Emergent Serious Adverse Events by MedDRA System Organ Class and Preferred Term	FAS
Treatment Emergent Serious Adverse Events by MedDRA System Organ Class and Preferred Term	IMP
Overall Summary of Inoculum Emergent Adverse Events of Special Interest (AESI)	FAS
Overall Summary of Treatment Emergent Adverse Events of Special Interest (AESI)	IMP
Inoculum Emergent Adverse Events of Special Interest (AESI) by MedDRA System Organ Class and Preferred Term	FAS
Treatment Emergent Adverse Events of Special Interest (AESI) by MedDRA System Organ Class and Preferred Term	IMP
Summary of Concomitant Medications (FAS)	FAS
Summary of Concomitant Medications (IMP)	IMP
Haematology (Summary and Change from IMP Baseline)	FAS
Haematology (Categorical)	FAS
Cross-Tabulation of Haematology Abnormalities Versus IMP Baseline	FAS
Biochemistry (Summary and Change from IMP Baseline)	FAS
Biochemistry (Categorical)	FAS
Cross-Tabulation of Biochemistry Abnormalities Versus IMP Baseline	FAS
Liver Function: Summary of Participant Potentially Clinically Significant Abnormality	FAS
Liver Function: Summary of Peak Readings Since IMP Administration	FAS
Liver Function: Summary of Time to Peak Readings Since IMP Administration in Days	FAS
Urinalysis (Categorical)	FAS
Vital Signs Results and Change from IMP Baseline	FAS
Abnormal Vital Signs Results	FAS
ECG Results and Change from IMP Baseline	FAS
ECG QTc Categorical Analyses	FAS
ECG Clinical Assessment	FAS

MMV_PYR_21_01 SAP_V1.1_06Feb23

Final Audit Report

2023-02-17

Created:	2023-02-16 (Australian Central Standard Time (Northern Territory))
By:	[name] ([contact])
Status:	Signed
Transaction ID:	CBJCHBCAABAkV7vApbvRoRStFhB2QHJ3BrAw8SU8fhC

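### SAP Table B sets the post-pyronaridine laboratory, liver, vital-sign and ECG summaries on everyone inoculated, although undosed participants have no treatment baseline

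*SAP*

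**What the plan says.** **Analysis sets (SAP 5.1).** "The Full Analysis Set (FAS) will consist of all enrolled participants, i.e. participants that received the malaria challenge agent". By contrast, "The IMP Set will include all enrolled participants administered with the IMP".

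**Table allocation (SAP Appendix, Table B).** The FAS stands against every haematology, biochemistry, liver-function, urinalysis, vital-sign and ECG summary table. That includes tables whose content is defined by dosing: "Liver Function: Summary of Peak Readings Since IMP Administration", its time-to-peak companion, "Vital Signs Results and Change from IMP Baseline", the matching haematology, biochemistry and ECG tables, and the abnormality cross-tabulations. The treatment-emergent AE, SAE and AESI tables use the IMP Set, apart from one row whose title mixes inoculum-related and treatment-emergent. SAP 11.3 says safety data will draw on both sets but does not say which table uses which.

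**Baselines.** SAP 4.2.2 defines one safety baseline before inoculation and one before the first pyronaridine dose. The laboratory summaries are described as "including observed values, absolute change from treatment baseline" (SAP 11.3.3), and SAP 11.4 to 11.6 likewise use only the treatment baseline. Protocol 9.4.4 says: "Summary tables for each scheduled visit, including observed values, change from each baseline and clinical significance of each abnormal value, will be presented". SAP 13 reports no change to the planned analysis.

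**Undosed participants.** Protocol 7.1.1 lists grounds for giving rescue treatment instead of pyronaridine on Day 8. One begins "A participant has an ALT or AST" and sets the limit at more than twice the upper limit of normal (ULN), or total bilirubin above the ULN. Another is QTcF above 480 msec. Scheduled haematology and biochemistry then continue to Day 29±1.

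**The concern.** The secondary safety endpoint concerns pyronaridine from Day 8 onward. Protocol 2.2.1 attributes the ALT rises seen with the artesunate combination mainly to pyronaridine, and also says malaria infection itself raises liver tests. A liver table meant to show possible drug toxicity should therefore keep dosed and undosed participants apart, especially since some of the undosed are selected for abnormal liver tests. A table that combines an inoculated population with a dosing-based baseline does not do this, and it disagrees with the set used for treatment-emergent AEs in the same appendix. With at most 18 participants, one or two people visibly move a percentage.

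The baseline omission matters for a related reason. Protocol 7.1.1 expects mild ALT/AST and neutrophil changes after inoculation, so a Day 8 baseline may already contain an infection effect.

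**Working it through.** The plan states no figure on this point, so there is none to reproduce. The check compares the definitions with the table rows and then sizes the effect by illustration.

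**Inputs.** Maximum enrolment 18 (protocol 9.2). Percentage denominator: the number in the relevant population (SAP 4); the protocol's restriction to non-missing data (9.4.1) is not carried over. Number undosed, *u*, and number of dosed participants with a PCSA, *x*: not in the documents, assumed below.

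**1. What an undosed participant adds to each kind of row**

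| Row | Value from an undosed participant | Consequence |
|---|---|---|
| Peak, time to peak, change from treatment baseline | None: no dose time, no treatment baseline, no imputation (SAP 4) | Row set on the wrong population; statistics use non-missing values |
| Observed laboratory values by visit, categorical laboratory | Yes, sampling continues to Day 29±1 | Values pooled with those of dosed participants in Overall |
| Liver PCSA percentage | In the denominator; in the numerator only under one reading of the baseline | Dilution, possible over-counting |
| QTcF percentage | In the denominator; in the absolute 450/470 msec rows possibly in the numerator, since all scheduled and unscheduled visits count (SAP 11.6) | Dilution, possible over-counting |

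For vital signs and ECG the pooling of values is less certain, because protocol 7.1.1 lists no interim ECG or vital signs for undosed participants before the end-of-study visit.

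**2. Denominator effect.** IMP Set rate = *x*/(18 − *u*); FAS rate = *x*/18; their ratio is (18 − *u*)/18. With *x* = 2:

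| *u* | IMP Set | FAS, no undosed PCSA | FAS, every undosed participant a PCSA |
|---|---|---|---|
| 0 | 2/18 = 11.1% | 2/18 = 11.1% | 2/18 = 11.1% |
| 1 | 2/17 = 11.8% | 2/18 = 11.1% | 3/18 = 16.7% |
| 2 | 2/16 = 12.5% | 2/18 = 11.1% | 4/18 = 22.2% |
| 3 | 2/15 = 13.3% | 2/18 = 11.1% | 5/18 = 27.8% |

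**3. When the last column could apply.** SAP 11.3.3 counts a PCSA at any visit after baseline without naming the baseline. An undosed participant's event counts only if inoculation is meant. That participant must also meet a PCSA criterion. Withholding starts at ALT/AST above 2×ULN; PCSA needs above 5×ULN, or a bilirubin criterion, or above 2×ULN with symptoms such as fatigue, nausea or fever, or with eosinophilia. Those three symptoms or signs are also on the protocol's malaria list (8.1.3), so the overlap is possible but not automatic.

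**4. Which columns are affected.** SAP 4 and 4.2.4 give dose-group columns and an overall column, none for undosed participants. If randomisation is on Day 8 immediately before dosing (protocol 6.3, SAP 3.7), the undosed have no dose group and affect only Overall. Protocol 4.1 also places randomisation before Day 8; then they could sit in a dose-group column. In a group of two, as planned for Cohort 1, with one undosed and an event in the other, 1/1 = 100% becomes 1/2 = 50%.

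**5. Will anyone be undosed?** If each of 18 has an assumed chance *q* of being withheld, the chance of at least one is 1 − (1 − *q*)^18: 60% for *q* = 5%, 85% for 10%, 95% for 15%.

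**6. Baselines.** Protocol 9.4.1 defines two and 9.4.4 requires change from each. The SAP defines two and summarises change from one. This mismatch does not depend on *u*.

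**The case against.** Several points on the other side stand.

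- **The FAS is the protocol's own choice.** The protocol Safety Set is everyone inoculated (9.3), and 9.4.4 asks for descriptive safety statistics on it. Dropping the FAS tables would depart from the protocol, so the IMP Set tables should be added beside FAS summaries. The SAP has nevertheless already moved treatment-emergent AEs to the IMP Set.
- **Dosed-only liver events are partly covered.** The five PCSA criteria match the five hepatic AESI criteria in protocol 8.5.3, and treatment-emergent AESIs are tabulated on the IMP Set. A reader might infer that the main liver risk would go unreported; the documents do not support that.
- **No values mix in the peak and change rows.** A reader might infer from the table titles that undosed participants' readings enter these statistics. They cannot, because the reference time does not exist.
- **The larger percentages need two extra conditions.** A reader might take 22.2% as the expected distortion. It requires both withheld participants to meet a PCSA criterion and the unnamed baseline to be inoculation. The surrounding text in SAP 11.3.3 names only the treatment baseline, which is the more natural reading and leaves 11.1% against 12.5%.
- **Infection-phase changes are not hidden.** Observed values are summarised at each scheduled visit, individual results are listed, and inoculum-emergent AEs are tabulated on the FAS. What is missing is the summary of change from the inoculation baseline.

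**Conclusion.** The point holds as a mismatch between population and baseline. Table B sets dosing-based summaries on a population that may include people never dosed. For peak, time-to-peak and change rows the consequence is a wrong population without mixed values. For PCSA, categorical laboratory and QTcF percentages, the whole-population denominator dilutes the rate: 1.4 percentage points (12.5% − 11.1%) with two of 18 undosed and two dosed events. Undosed participants' abnormalities could also be counted while the PCSA baseline is unnamed and the QTcF table takes every visit.

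The effect falls mainly in the Overall column, reaches the dose-group columns only if randomisation precedes Day 8, and is zero if nobody goes undosed. The documents do not give the number undosed, so all percentages are illustrations. Confidence is high on the table allocation and lower on the numerical effect.

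The second finding is independent of that number: the SAP omits the change from inoculation baseline required by protocol 9.4.4, while SAP 13 declares no change. Both should be corrected; neither affects the primary PK/PD analysis.

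**What to change.** 1. In Table B, present on the IMP Set every table defined by time since dosing or change from the treatment baseline, the cross-tabulations against that baseline, the liver PCSA, peak and time-to-peak tables, and the QTcF categorical table.
2. In SAP 11.3.3 and 11.6, state that PCSA and QTcF events are counted after the treatment baseline.
3. Keep FAS summaries, since the FAS contains the same people as the protocol's Safety Set. Add change from the inoculation baseline for laboratory, vital-sign, body-measurement and ECG data, and show undosed participants in their own column or listing.
4. Reconcile the two statements on the time of randomisation, so that it is clear whether an undosed participant can carry a dose group.
5. Record in SAP 13 any departure from protocol 9.4.4 that remains.

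The cost is SAP text, table shells and programming of data already collected. No new visits, samples or participants are needed.
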